9.7.2.2 Missing or Incomplete Data and Lost to Follow-up

Responses to questions in the HCP questionnaires may be missing. They will be dealt with in two ways:

- In the primary analysis, missing data will be ignored.
- As a sensitivity analysis, a conservative assumption will be made in which missing values will be considered as incorrect or worst responses.

For questions without a correct or best response, missing data will be ignored in the analysis.

Approved

9.7.2.3 Descriptive Analysis

[figure not shown]
9.7.2.3.1 Description of Study Enrollment

The study populations as identified in the recruitment process for each of the HCP surveys will be described. Recruitment rates and a description of the number of subjects in the study and analysis populations will be provided.

Analysis sets: As shown in [Figure 2](#), datasets for analysis will be further described in the SAP and will include:

- Study population: Physicians, nurses and pharmacists identified and potentially willing/eligible to participate.
- Eligible Set: All physicians, nurses and pharmacists who fulfill the eligibility criteria.
- Enrolled Set: All eligible physicians, nurses and pharmacists who agree to participate in the study and access the electronic survey.
- Full Analysis Set: All physicians, nurses and pharmacists who complete the questionnaire of their corresponding survey and have valid responses to allow for the assessment of the primary objective.

Figure 2. Study Population and Datasets Flow-chart

9.7.2.3.2 Description of Physicians, Nurses and Pharmacists Characteristics

For each survey, the following sociodemographic characteristics will be summarized: age group, gender, country and experience. Participation in Blincyto clinical trials and time since last contact with a patient receiving Blincyto will also be described.

Approved

9.7.2.4 Analysis of the Primary, Secondary and Exploratory Endpoint(s)

The primary analysis for each survey will be performed for the endpoints below described, and will include the total number of HCPs with valid responses to all relevant questions and the percentage of HCPs with a positive response for the endpoint:

- **Receipt** will be described through the percentage of physicians, nurses and pharmacists who report having received the brochure.
- A mean **knowledge** score will be created to summarise individual physician, nurse and pharmacist scores. An individual physician, nurse or pharmacist score is calculated as the proportion of all knowledge questions with correct responses.
- A mean **behaviour** score will be created to summarise individual physician, nurse and pharmacist scores. An individual physician, nurse or pharmacist score is calculated as the proportion of all behavior questions with correct responses. For physicians and nurses, the score will also include the adequacy of the timing for the distribution of the card and brochure to patients/caregivers. Among those who do not distribute the materials to patients/caregivers, a categorical variable will describe the reasons for non-compliance.
- Correlation of total scores for questions of knowledge and behaviour.

The secondary analyses are:

- Among physicians, nurses and pharmacists who have read the educational materials, an ordinal scale will describe the self-reported level of **understanding**.
- **Usage** will be assessed with the percentage of physicians, nurses and pharmacists who have read the material. Among those physicians, nurses and pharmacists who have read the brochure, an ordinal scale will assess how often the material was referred to. Among those who do not read the materials, a categorical variable will describe the reasons for not reading them.

9.7.2.5 Sensitivity Analysis

9.7.2.5.1 Subgroup Analysis

The results will be presented overall and by country, whether the materials were read or not, time since last contact with a patient receiving Blincyto and participation in Blincyto clinical trials.

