Surveyed HCPs will arise from approximately [REDACTED] centres however it may be more or less depending on recruitment.

- **Data Analysis**

Categorical data will be summarized by counts and percentages. Continuous data will be summarized using number, mean, standard deviation (SD), median, quartiles, minimum and maximum and in the case of non-normally distributed data, median, range and interquartile range. All 95% confidence intervals will be presented to three decimal places.

Analyses will be mainly descriptive for the overall study population and certain subgroups, such as those who read the material vs. those who did not. The statistical analysis will include a summary of the study conduct, a descriptive analysis and the analysis of the objectives.

Receipt will be described through the percentage of physicians, nurses and pharmacists who report having received the brochure.

Knowledge: A mean score will be created to summarise individual physician, nurse and pharmacist scores. An individual physician, nurse or pharmacist score is calculated as the proportion of all knowledge questions with correct responses.

Behaviour: A mean score will be created to summarise individual physician, nurse and pharmacist scores. An individual physician, nurse or pharmacist score is calculated as the proportion of all behavior questions with correct responses. For physicians and nurses, the score will also include the adequacy of the timing for the distribution of the card and brochure to patients/caregivers. Among physicians and nurses who do not distribute the materials to patients/caregivers, a categorical variable will describe the reasons for non-compliance.

Understanding: Among physicians, nurses and pharmacists who have read the educational material, an ordinal scale will describe the self-reported level of understanding.

Usage will be described with the percentage of physicians, nurses and pharmacists who have read the material. Among those physicians, nurses and pharmacists who have read the educational material, an ordinal scale will assess how often the material was

Approved

referred to. Among those who do not read the materials, a categorical variable will describe the reasons for not reading them.

Correlation of total scores for questions of knowledge and behaviour.

5. Amendments and Updates

None

6. Milestones

Milestone	Planned date
[REDACTED]	[REDACTED]
[REDACTED]	[REDACTED]
Start of data collection*	Feb 2017
[REDACTED]	[REDACTED]

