9.2.3.1 Inclusion Criteria

- Physician, nurse or pharmacist has managed, administered or prepared Blincyto for at least one adult patient with Ph- R/R B precursor ALL.

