9.3.1 Outcome Assessment

The primary endpoints for the HCP survey are:

- Receipt: A categorical variable will describe the proportion of physicians, nurses and pharmacists who report having received the brochure.
- Knowledge: A mean score will be created to summarise individual physician, nurse and pharmacist scores. An individual physician, nurse or pharmacist score is calculated as the proportion of all knowledge questions with correct responses.
- Behaviour: A mean score will be created to summarise individual physician, nurse and pharmacist scores. An individual physician, nurse or pharmacist score is calculated as the proportion of all behavior questions with correct responses. For physicians and nurses, the score will also include the adequacy of the timing for the distribution of the card and brochure to patients/caregivers. Among physicians and nurses who do not distribute the materials to patients/caregivers, a categorical variable will describe the reasons for non-compliance.

The secondary endpoints for the HCP survey are:

- Understanding: Among physicians, nurses and pharmacists who have read the educational materials, an ordinal scale will assess the self-reported level of understanding.
- Usage: A categorical variable will describe the proportion of physicians, nurses and pharmacists who report having read the brochure. Among those physicians, nurses and pharmacists who have read the educational material, an ordinal scale will assess how often the material was referred to. Among those who do not read the materials, a categorical variable will describe the reasons for not reading them.

Approved

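### As worded, the read/not-read subgroup pools HCPs who never received the brochure with recipients who did not read it, so the group's knowledge and behaviour scores cannot be attributed to either

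*Protocol*

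**What the plan says.** Section 9.7.2.5.1 sets the subgroups: "The results will be presented overall and by country, whether the materials were read or not". The full list after country is "whether the materials were read or not, time since last contact with a patient receiving Blincyto and participation in Blincyto clinical trials". Receipt is not in the list. The Data Analysis part of the abstract (section 4) names the same two-level split as its example: "certain subgroups, such as those who read the material vs. those who did not".

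Receipt and reading are separate endpoints. In section 9.7.2.4, receipt (primary) "will be described through the percentage of physicians, nurses and pharmacists who report having received the brochure", and usage (secondary) "will be assessed with the percentage of physicians, nurses and pharmacists who have read the material". Section 9.3.1 words usage in the same way: "A categorical variable will describe the proportion of physicians, nurses and pharmacists who report having read the brochure". Neither place limits the usage percentage to recipients. On reasons, section 9.7.2.4 says: "Among those who do not read the materials, a categorical variable will describe the reasons for not reading them".

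Section 9.2.3.1 admits an HCP who "has managed, administered or prepared Blincyto for at least one adult patient with Ph- R/R B precursor ALL". Receipt of the brochure is not a condition.

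**The concern.** Section 8 asks separately whether the brochures reached their target population and whether they are used as intended. Section 9.1 justifies the timing of the survey by the chance to correct weak parts of the educational programme early. Not reaching HCPs and not being read by those reached are different weaknesses with different remedies.

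Knowledge and behaviour are primary endpoints and part of the success statement in section 8.2. The only planned view of these scores by brochure exposure is read against not read. If the not-read group contains both kinds of HCP, a low score there could come from people who never had the material or from people who had it and left it unread. A high score could come from recipients who skipped it because they already knew the product. The balance between the two also depends on how well distribution worked, so the same label can describe different groups in different countries.

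**Working it through.** **Is the pooling what the text says?** Three statements side by side:

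1. Non-recipients can enrol (9.2.3.1).
2. The subgroup has two levels, read or not (9.7.2.5.1 and the abstract).
3. Percent read is stated over physicians, nurses and pharmacists with no restriction (9.3.1, 9.7.2.4). Where a restricted denominator is wanted, the protocol says so: understanding and frequency of referral are limited to those who have read the material.

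On the plain reading, an enrolled HCP who never received the brochure falls under not read.

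**How large is the effect?** The protocol gives no figure to reproduce, so this is an illustration.

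Inputs:
- n = 50, inside the 40 to 60 physicians and pharmacists in the caption of Table 3.
- Receipt r = 60% and 90%, the planning range in section 9.5.
- Reading rate among recipients q: not in the protocol; assumed 90%, 70% and 50%.
- Only recipients read: an assumption.

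Formulas: read = n·r·q; never received = n(1−r); received but unread = n·r(1−q); never-received share of the not-read group = (1−r)/(1−rq). The share does not depend on n, so it applies to the nurse survey too.

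| q (assumed) | r | Read | Never received | Received, unread | Not read | Never-received share |
|---|---|---|---|---|---|---|
| 90% | 60% | 27 (54%) | 20 | 3 | 23 | 20/23 = 87% |
| 90% | 90% | 40.5 (81%) | 5 | 4.5 | 9.5 | 5/9.5 = 53% |
| 70% | 60% | 21 (42%) | 20 | 9 | 29 | 20/29 = 69% |
| 70% | 90% | 31.5 (63%) | 5 | 13.5 | 18.5 | 5/18.5 = 27% |
| 50% | 60% | 15 (30%) | 20 | 15 | 35 | 20/35 = 57% |
| 50% | 90% | 22.5 (45%) | 5 | 22.5 | 27.5 | 5/27.5 = 18% |

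**What this does to the score.** The mean of the not-read group is w·m₀ + (1−w)·m₁, where w is the never-received share, m₀ the mean of non-recipients and m₁ the mean of recipients who did not read. If m₀ and m₁ differ by one point (assumed), moving from 60% to 90% receipt shifts the pooled mean by 0.87 − 0.53 = 0.34 points at q = 90%, and by 0.57 − 0.18 = 0.39 points at q = 50%. Nobody's knowledge has changed.

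**Same split, different group.** Two assumed settings at n = 50, expected counts:
- A: receipt 70%, 80% of recipients read. Read 28; not read 22, of whom 15 never received and 7 received.
- B: receipt 95%, 59% of recipients read. Read 28; not read 22, of whom 2.5 never received and 19.5 received.

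Both give 28 read and 22 not read, but never-recipients are 15/22 = 68% of the not-read group in A and 2.5/22 = 11% in B.

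**What the other endpoints recover.** The receipt endpoint does tell A from B: 35/50 = 70% (Clopper-Pearson 95% CI 55.4 to 82.1) against 48/50 after rounding (86.3 to 99.5). Received minus read gives the proportion who received but did not read: 70% − 56% = 14% in A and 95% − 56% = 39% in B. Neither recovers knowledge and behaviour scores for the two components.

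**The case against.** A reader might infer that the plan cannot tell a distribution failure from a usage failure. The protocol does not support that. Receipt is a primary endpoint for each HCP type, percent read is a secondary endpoint, and reasons for not reading are tabulated. If only recipients read, dividing percent read by receipt gives the reading rate among recipients: 54%/60% = 90% in the first row of the table. If the subgroup results include receipt, receipt within the not-read group would be shown as well.

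Nor is read/not read the only internal comparison. Country, time since last contact and trial participation are also planned. Low receipt does not settle the usage question either, because frequency of referral is already limited to readers.

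The pooling is read from the wording and is not stated outright. Section 9.9 mentions skip patterns, and the questionnaires listed in Appendix A are not shown. If the reading item is put only to recipients, non-recipients would fall outside the not-read group. Section 9.7 leaves detailed methods and table shells to the SAP.

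The study is descriptive, section 9.9 calls subgroup analyses exploratory and possibly unreliable, and Appendix B says no exposure-outcome association will be assessed. As a pure exposure contrast, read/not read can be defended, since neither component has read the brochure. A split would not isolate the brochure from the SmPC, which the brochures in Appendix F say comes with them. The received-but-unread cell could also be too small to be useful.

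Most of this stands and limits the point. It does not remove it. The protocol itself names a two-level variable and an unrestricted usage percentage, and nothing in the plan yields the scores separately for non-recipients and for recipients who did not read.

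**Conclusion.** The point holds in a limited form. As worded, the only planned contrast of knowledge and behaviour by brochure exposure has a comparison group of mixed origin, and its scores cannot be attributed to either component. Over 60% to 90% receipt and an assumed 50% to 90% reading among recipients, never-recipients make up between 18% and 87% of that group.

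This rests on the plain reading of the subgroup and usage wording, on the assumed reading rates, and on only recipients reading. The last is not stated, and colleagues in one centre could share a copy. No primary result changes, and aggregate receipt and usage remain interpretable. It is a low-cost improvement to an exploratory breakdown and worth making because those scores feed the judgement of the programme.

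**What to change.** - **9.7.2.5.1 and the abstract:** replace the two-level split with three levels: not received; received and not read; read. State how an HCP who read a copy without personally receiving one is classed. Present knowledge and behaviour by these levels.
- **9.3.1 and 9.7.2.4:** report percent read both among all HCPs and among recipients. The first measures reach and the second uptake; there is no need to choose between them. Tabulate reasons for not reading among recipients.

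Receipt and reading are already to be collected, so the cost is wording and one more table column. The drawback is a small cell: with 50 HCPs and 90% of recipients reading, received-but-unread holds about 3 (at 60% receipt) to 4.5 (at 90% receipt) HCPs per survey. Show that level descriptively with its counts and draw no comparison from it when it is that small.

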9.8 Quality Control

Standard operating procedures will be applied to ensure quality to all aspects of the study conduct, data management and statistical analysis.

In addition, data generated by these surveys must be available for inspection upon request by representatives of national and/or local health authorities, sponsor monitors, representatives, and collaborators, as appropriate. The investigator must notify Amgen promptly of any inspections scheduled by regulatory authorities, and promptly forward copies of inspection reports to Amgen.

Approved

9.9 Limitations of the Research Methods

HCPs who refuse to participate may limit the representativeness of the HCP survey. Selection of nurses and pharmacists will be dependent on the cooperation of physicians in centres.

HCP responses may be biased by referral to the brochures as they complete the questionnaire. This may be minimized by explaining that responses should be based on assessing what they currently know and that they should not refer to the brochures.

Measures to minimize HCP response bias with online questionnaires are: all questions are programmed to ensure that they are presented in an appropriate sequence, questions must be answered in sequence, skipping ahead to later questions is not permitted, questions cannot be changed once submitted, and skip patterns to questions are clearly indicated.

Self-reporting of actions and behavior may be biased towards positive values. The development of a questionnaire carefully pre-tested before actual study starts aims to minimize such a bias. Non-response of items should be minimized due to the rigorous process of questionnaire development, validation and testing.

Recall bias is an inherent limitation of questions asking about the past. This will be assessed by time since last contact with a patient receiving Blincyto, or its preparation.

The size of the study populations will allow an acceptable level of precision (considering the rarity of the disease) for the study primary endpoints. However, subgroup analyses will be exploratory and may be unreliable due to the small number of patients.

10. Protection of Human Subjects

10.1 Informed Consent

Consent for the surveys will be obtained online before completing the questionnaire. Those who decline to participate will not be able to access the questionnaire.

10.2 Institutional Review Board (IRB)/Independent Ethics Committee (IEC)

Local approvals from ethics committees are not required as only data from HCPs and not clinical data from patients, will be collected.

10.3 Subject Confidentiality

For the purposes of protecting a HCPs identity, a unique code will be assigned to each HCP, such as a series of numbers and/or letters (for example, CA180330-0001-00001). The data that are recorded with the HCP's assigned code are called "key-coded data".

Approved

Key-coded study data will be managed by the sponsor and/or its delegates in a study-specific electronic database (the “study database”). Only the investigator and the site staff have access to the link between HCP’s assigned code and the identity. Data that could directly identify the HCPs will not be collected in the “study database”.

The HCP’s personal data which may be included in the recruitment and study databases will be treated in compliance with all local applicable laws and regulations. When archiving or processing personal data pertaining to the HCPs, all appropriate measures to safeguard and prevent access to this data by any unauthorized third party will be taken.

11. Collection of Safety Information and Product Complaints

As the questionnaire is on-line with no free-text questions, very few reports of adverse events and medication errors for Blincyto are expected.

11.1 Definition of Safety Events

11.1.1 Adverse Events

An adverse event is any untoward medical occurrence in a subject/patient administered a pharmaceutical product(s) irrespective of a causal relationship with this treatment.

An adverse event can therefore be any unfavorable and unintended sign (including an abnormal laboratory finding, for example), symptom, or disease temporally associated with the use of a product(s), whether or not considered related to the product(s). The definition of an adverse event includes:

- Worsening of a pre-existing condition or underlying disease
- Events associated with the discontinuation of the use of a product(s), (eg, appearance of new symptoms)

It is the HCP’s responsibility to evaluate whether an adverse event is related to Blincyto prior to reporting the adverse event to Amgen.

11.1.2 Serious Adverse Events

A serious adverse event is any adverse event as defined above that meets at least one of the following serious criteria:

- is fatal
- is life threatening (places the subject at immediate risk of death)
- requires in-patient hospitalization or prolongation of existing hospitalization

Approved

- results in persistent or significant disability/incapacity
- is a congenital anomaly/birth defect
- is an “other significant medical hazard” that does not meet any of the above criteria

A hospitalization meeting the regulatory definition for “serious” is any in-patient hospital admission that includes a minimum of an overnight stay in a healthcare facility.

“Other significant medical hazards” refer to important medical events that may not be immediately life-threatening or result in death or hospitalization, but may jeopardize the subject or may require intervention to prevent one of the other outcomes listed in the definition above. Examples of such events could include allergic bronchospasm, convulsions, and blood dyscrasias, drug-induced liver injury, events that necessitate an emergency room visit, outpatient surgery, or other events that require other urgent intervention.

11.1.3 Other Safety Findings

Other Safety Findings (regardless of association with an adverse) include:

- Medication errors, overdose, whether accidental or intentional, misuse, or abuse, , involving an Amgen product,
- Pregnancy and lactation exposure,
- Transmission of infectious agents,
- Reports of uses outside the terms for authorized use of the product including off-label use,
- Occupational exposure,
- Any lack or loss of intended effect of the product(s).

11.1.4 Product Complaints

Product Complaints include any written, electronic or oral communication that alleges deficiencies related to the identity, quality, durability, reliability, safety, effectiveness, or performance of a product or device after it is released for distribution to market or clinic by either Amgen or by distributors and partners for whom Amgen manufactures the material. This includes any drug(s) or device(s) provisioned and/or repackaged /modified by Amgen. Drug(s) or device(s) includes investigational product.

